1) **Protocol Title:** Combining Lovastatin and a Parent-Implemented Language Intervention in a Multi-Modal Treatment of Fragile X Syndrome

2) Autl	nor of Protocol
XUC	C Davis Researcher
□ Re	searcher from other institution
□ Pr	ivate Sponsor
	operative Group
□ Ot	-

3) Objectives

Aim 1. Test the efficacy of a 20 week multi-modal treatment comprised of lovastatin and the Parent-implemented Language Intervention (PILI) for children with FXS. Children will be randomized to drug or placebo in a double-blind design with all participating in the PILI. The primary endpoint will be a spoken language composite and the secondary endpoint will be challenging behavior. We will test the following hypotheses:

Hypothesis 1a. Improvements in spoken language and behavior will be greater among lovastatin-treated than placebo treated participants.

Hypothesis 1b. Improvements in parental use of the PILI-targeted strategies will be associated with greater improvements in child language and behavior, especially in the lovastatin-treated group, thereby demonstrating benefit of the combined intervention.

Aim 2. (a) Identify biomarkers in peripheral immune cells associated with FXS and the efficacy of treatment and (b) elucidate the cellular/molecular mechanisms by which lovastatin influences MEK/ERK and Rho GTPase signaling pathways and immunological abnormalities associated with FXS.

Hypothesis 2a. Lovastatin corrects core biochemical and physiological impairments by normalizing Ca2+dependent and/or Ca2+-independent regulation of the MEK/ERK signaling pathway.

Hypothesis 2b. Lovastatin normalization of MEK/ERK signaling and/or Rho GTPase signaling is mediated by its effects on isoprenoid synthesis.

Hypothesis 2c. Individuals with elevated inflammatory cytokines will be more responsive to lovastatin.

4) Background

This is the first multi-modal treatment to combine a targeted treatment for FXS, lovastatin, with an innovative parent-implemented intervention (PILI) targeting language and challenging behavior delivered through telehealth technology. Our hypothesis is that targeted treatments will be more effective when applied in combination with PILI. We also will examine whether changes in the activity of key

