pathways/proteins influenced by FMRP (the mitogen-activated protein kinase (ERK) and MMP-9) are biomarkers of treatment responsiveness. Because lovastatin is also an anti-inflammatory, we will characterize MEK/ERK signaling in peripheral immune cells both and pre- and post- treatment to determine whether levels of these signaling molecules are predictive biomarkers of treatment response. We hypothesize that those individuals with elevated inflammatory cytokine profiles will be most responsive to lovastatin treatment. Once modeled in FXS, results from these studies can then be applied to other neurodevelopmental disorders including Rasopathies.

Lovastatin as a treatment for FXS: Lovastatin is an inhibitor of the rate-limiting enzyme in cholesterol biosynthesis and an FDA-approved treatment for hyperlipidemia. Lovastatin has also been proposed as a treatment for IDD, particularly for Rasopathies and Neurofibromatosis Type 1 (NF1). Lovastatin reduces activation of the small guanosine triphophatase (GTPase) Ras, which in turn reduces activity of the MEK/ERK signaling pathway. Lovastatin interferes with recruitment of Ras to the membrane, a process required to transition from inactive GDP to active GTP. The interaction of Ras with the membrane requires the prost-translational addition of a farnesyl group to the C terminus of Ras, and lovastatin inhibits Ras farnesylation by targeting the upstream mevalonate pathway.

Recent extensions of animal studies to FXS have been promising. In a study of Fmr1 knock out (KO) mouse, intraperitoneal injections of lovastatin protected the mice from audiogenic seizures that are part of the FXS phenotype. In the KO mouse, the lack of FMRP represents a loss of the translational repressor for many proteins important for synaptic plasticity. Lovastatin corrected the excessive protein production in the KO mouse, inhibited RAS-ERK1/2 signaling in hippocampal neurons, and improved the phenotype. Although lovastatin has been used to treat children as young as one year of age, FDA approval extends only to 10- to 17-years-olds and studies of efficacy for cognitive impairments in NF1 have shown benefit and safety for this age range so this study will focus on the same age group.

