Once eligibility is confirmed, subjects will be approached to obtain their authorization to access and use their health information for the research. Please see Section 14 for additional information regarding Data Management and Confidentiality.

8) Compensation to the Subjects

Subjects will not be compensated for their participation. Possible expenses to the subject's family include time spent at the clinic as well as expenses for travelling. Therefore subjects who would otherwise not be able to participate may be eligible for travel reimbursement for travel costs incurred as specified in question 25.

9) Study Timelines

We anticipate seeing 30 pilot participants in the first 18 months under consent form C. During this same time period up to an additional thirty participants and their mothers will be seen under consent form A, phases 1 and 2 of the study. During Phase 3, 50 participants and their parent/caregiver will be recruited into the clinical trial portion utilizing consent form B. In addition, 3 subjects will be recruited into phase 4, under consent form D. Phases 2,3, and 4 of the study, using consent forms A, B and D, will occur over the last 3.5 years of the project).

10) Study Endpoints

The primary outcome measure is a spoken language composite measured at baseline and at the end of treatment. Comparison of the two treatment groups on the outcome measure will be made through analysis of covariance, adjusted for baseline values on that measure using an intent-to-treat approach. Two-sided tests will be used with alpha at .05. With this sample size, power to detect a moderate effect size of 0.6 will be 80%, assuming equal standard deviations in the groups. The assumptions we are making to estimate power are conservative as evidenced by recent published tests of a parent mediated intervention for autism (Rogers et al., 2012) and a randomized controlled trial of a drug in FXS (Berry-Kravis et al., 2012), with samples sizes of 98 and 60, respectively, and behavioral outcome measures.

Analysis of our secondary outcome measure, the social avoidance subscale of the FXS- normed ABC, as well as the exploratory VAS and CGI will follow the same approach as the primary analysis. Additional analyses will examine potential child moderators of response to lovastatin (age, Leiter, ADOS symptom severity) using linear regression.

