Aim 1. Hypothesis 1b. We will use linear regression to test the relationships between parent behaviors and child outcome at 20 weeks (i.e., spoken language composite). The regression will include main effect terms for both treatment and parent behavior as well as the interaction term, while controlling for baseline values of the parent and child measures. Various parent confounders will be

evaluated as well (e.g., SCL-90-R severity score). The main effect of the parent behavior will test the contribution of PILI, whereas the interaction term will test the value of the combined treatment. These analyses will be done separately with two parent behavior measures (parent verbal responsiveness composite and quality of caregiver involvement score).

Analyses will be repeated for secondary outcome measures.

Aim 2. In the addressing hypotheses 2a, b, and c, we will identify biomarkers associated with FXS using a regression model for marker expression with grouping of phenotype (i.e., disease state or respond to treatment) as a predictor with important clinical cofounders as covariates. The marker performance will be evaluated using receiver operating characteristic (ROC) curves to test which biomarkers are statistically better diagnostic and prognostic tests for FXS. We will further develop predictive signatures of elements involved in MEK/ERK and Rho GTPase signaling pathways in response to lovastatin using PAM, or other pattern recognized methods. The potential biomarkers are phosphorylation of S6K1, AKt, EIF4E, and ERK/MEK as well as levels of IL-1, IL-6, IL- 10, MCP-1, IL-1alpha, IL-1beta, MMP-9, and MIF.

Based on the findings of [name] et al. (2016, American Journal on Intellectual and Developmental Disabilities) statistical power for this study is expected to be sufficient with a subject enrollment of 50. In the [name] study, a treatment effect was demonstrated with the same outcome measure and same age range in a sample size of 10 per group. In this multimodal study, it is expected that the effect of the drug, if it is to be clinically meaningful, will be at last as large as the effect of the language intervention by itself in the 2016 study. In fact, the expectation is to see expect synergistic effects with the language intervention amplifying the effect of the drug.

11) Procedures Involved

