Cytokine and chemokine levels will be measured in plasma using a Luminex based multiplex technology to analyze IL-1, IL-6, IL-10, MCP-1, IL-1alpha, IL-1beta, MMP-9 levels, and MIF. These will be measured using plasma according to the manufacturer's instructions. A control plasma sample will be run on each plate for normalization between plates. The plates will be read on a Bio-Plex 100 (BioRad) and analyzed using Bio-Plex Manager software using a 6-point standard curve. Levels of cytokines and chemokines that fall below the limit of detection (LOD) are assigned a value of LOD/2 to allow for log_n transformation of raw data. Plasma levels of TGF- beta will be determined by ELISA as previously described (Ashwood et al., 2008).

To determine the effects of lovastatin treatment on TLR4 activation, we will use isolated PBMCs and stimulate the TLR4 receptor with LPS for 48 hr. The supernatants will be collected and analyzed for IL-1, TNF-alpha, IL-6, MMP-9, and MIF using luminex multiplex analysis. Quantification of Molecular Biomarkers: MMP-9 activity will be measured in plasma of participants, which will be obtained from whole blood samples by centrifugation and aliquots will be stored at -80°C until use. Samples will be coded and the code revealed after results have been obtained. MMP activity will be quantified by zymogram analysis. Levels of total and phosphorylated ERK ½ will also be assessed by Luminex. In addition, kinetic analysis of the early phases of ERK activation will be employed to determine the feasibility of using pERK in PMBCs as an indicator for responsiveness to lovastatin treatment. PMBCs will be isolated from CPT tubes, counted, and stimulated by PMA to activate protein kinase C-mediated phosphorylation of ERK. Cells will be fixed at different time points by the addition of methanol, permeabilized and immunostained for phospho- ERK and analyzed in a flow cytometer as described in Weng, et al. (2008).

The mechanistic effects of lovastatin on MEK/ERK signaling and Rho GTPase activation will also be studied. The goal of these studies is to determine: (1) the

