effects of lovastatin on Ras GTPase and Rho GTPase (RhoA, Cdc42 and Rac1) activation in antigen presenting cells (APCs); (2) the effects of lovastatin on Ca2+ signaling in APCs; and (3) the relative contribution of cholesterol versus isoprenoid synthesis inhibition to lovastatin effects on these signaling events in APCs. The data obtained in these mechanistic studies will provide insight on therapeutic targets which may be useful in developing more targeted treatments and provide the groundwork for expanding this work into relevant animal models to examine mechanisms by which lovastatin improves neurodevelopmental outcomes. APCs will be isolated from PBMCs collected from children with FXS (where baseline values will be compared to treatment samples) by panning for cells that adhere to a polystyrene tissue culture dish. High content imaging, which enables cell based detection of up to five distinct fluorescent markers simultaneously in a multi-well format plates (up to 96 wells per plate) will be used to determine: 1) specific APCs as identified by cell surface markers (as described in Enstrom et al., 2010); and 2) activation of Ras and Rho GTPases as identified by immunocytochemical localization of these signaling molecules within the cell, with activated versus inactivated forms indicated by plasma membrane versus cytoplasmic localization, respectively (Bar-Sagi and Hall 2000).

Real-time Ca2+ oscillations measured with FLIPR will also be studied. This rapid throughput technique will be used to measure the onset and properties of synchronized Ca2+ oscillations in human monocyte cell cultures at baseline, midtreatment, at the end of the trial. This method permits simultaneous measurements of intracellular Ca2+ transients in a 96-well format using the FLIPR® Tetra imager rapidly (10Hz) and in real-time as we described recently (Cao et al 2012). Cells are loaded with Fluo-4 and recordings from each of 96-wells are simultaneously acquired for 10 min. We will analyze Ca2+ responses evoked by ATP challenges (1-200 μ M) in monocytes to correlate whether differential responses are correlated with treatment response as well as cytokine/chemokine profiles.

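### Aim 2 asks what lovastatin does to signalling markers in the children's own cells but writes no comparison by randomised arm, so a shift common to both arms could be read as a drug effect

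*Combined protocol and SAP*

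**What the plan says.** **The question.** Hypothesis 2a (Section 3) is causal: "Lovastatin corrects core biochemical and physiological impairments by normalizing" the regulation of MEK/ERK signalling. The mechanistic part of Section 11 (b) sets three goals. The first is to determine the "effects of lovastatin on Ras GTPase and Rho GTPase (RhoA, Cdc42 and Rac1) activation in antigen presenting cells (APCs"). The second asks the same of calcium signalling in those cells. The third asks how far cholesterol or isoprenoid synthesis accounts for the effects.

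**The comparison given.** For the antigen-presenting cells used in the Ras/Rho imaging, Section 11 (b) says: "APCs will be isolated from PBMCs collected from children with FXS (where baseline values will be compared to treatment samples"). It does not say whether these samples come from lovastatin children only or from both arms. The Background (Section 4) also describes a before-and-after look, to "characterize MEK/ERK signaling in peripheral immune cells both and pre- and post- treatment", there with the aim of finding predictors of response.

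**The statistical model.** Section 10 covers Hypotheses 2a, 2b and 2c in one paragraph, "using a regression model for marker expression with grouping of phenotype (i.e., disease state or respond to treatment) as a predictor". It then adds ROC curves and "predictive signatures of elements involved in MEK/ERK and Rho GTPase signaling pathways in response to lovastatin using PAM" or similar methods. Randomised arm is not named in any of these.

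**The between-arm analysis that does exist.** For Aim 1, Section 10 says: "Comparison of the two treatment groups on the outcome measure will be made through analysis of covariance", adjusted for baseline. The same approach is extended by name to the ABC social avoidance subscale, the VAS and the CGI. Biomarkers are not on that list.

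**The samples.** The trial is double-blind and placebo-controlled, and every child receives the parent-implemented language intervention (PILI). The schedule in Section 11 (b) marks biomarkers at all three visits, with no restriction to one arm.

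**The concern.** A change from baseline in a treated child contains the drug effect and everything else that moved over 20 weeks. Here that could include maturation in 10- to 17-year-olds, the PILI, and assay drift between visits. For the plasma Luminex assays the plan guards against drift: "A control plasma sample will be run on each plate for normalization between plates". No equivalent is described for the imaging of antigen-presenting cells.

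The Section 10 regression does not repair this. Response to treatment is a grouping formed after randomisation. Because all children receive the PILI, it can occur in either arm. A marker difference between responders and non-responders says whether the marker tracks outcome. It does not say whether lovastatin moved the marker.

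At stake is whether Aim 2 can support a statement that lovastatin changed signalling in these children. The design provides the control needed for that statement, but no written analysis uses it.

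**Working it through.** The documents state no sample size, power or error rate for Aim 2, so there is no figure of the plan's to reproduce. The calculation below shows only how a before-after test behaves when there is drift and no drug effect.

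**Inputs**
- Children in the clinical trial: up to 50 (Section 6). Half receive lovastatin (Section 17), so n = 25 per arm.
- Two-sided alpha 0.05: stated in Section 10 for Aim 1; assumed here for Aim 2.
- Test form: a paired t-test of baseline against treatment sample. This is an assumption, since the plan names no test for this comparison.
- Drift k, common to both arms, in SDs of the within-child change: not in the documents; assumed range 0 to 0.5.
- True drug effect: zero.

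**Before-after test in the 25 lovastatin children.** The statistic follows a noncentral t with 24 degrees of freedom and noncentrality k × √25 = 5k. The rejection probability is P(|T| > t with 24 df at 0.975).

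**Comparison of change between arms.** The expected difference in change is k − k = 0, so the noncentrality is zero and the rejection probability is 5% at any k.

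| Drift k (SD of change) | Noncentrality 5k | Before-after, n = 25 | By arm, 25 v 25 |
|---|---|---|---|
| 0 | 0 | 5.0% | 5% |
| 0.1 | 0.5 | 7.7% | 5% |
| 0.2 | 1.0 | 16.1% | 5% |
| 0.3 | 1.5 | 30.2% | 5% |
| 0.5 | 2.5 | 67.0% | 5% |

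A simulation of 40,000 trials at k = 0, 0.3 and 0.5 gave 5.1%, 30.4% and 66.9% for the before-after test, and 5.0%, 5.0% and 4.9% by arm.

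**Price of the comparison by arm.** With SD of change s, the standard error of a within-arm mean change is s/√25 = 0.20s. For a difference between arms it is s × √(2/25) = 0.28s, larger by a factor of √2. The noncentrality for a true effect δ (in SDs of change) is δ × √(25/2). With 48 degrees of freedom, power is 55% at δ = 0.6 and reaches 80% at about δ = 0.81, before any gain from adjusting for the baseline marker.

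**The case against.** The strongest reply is that this is an inference from silence. Comparing treatment samples with baseline is the first step of any change-by-arm analysis, and coded samples would allow the second step. That is fair as far as intent goes: the documents do not show that the sponsor has decided against a comparison by arm. But the plan is not silent about method. It gives a before-after comparison for the Ras/Rho work, gives Aim 2 a model of its own, and lists the endpoints to which the between-arm analysis extends. Read as written, none of these compares markers by arm.

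The reply also limits the point. A reader might infer any of the following, and the documents do not support them:

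- **That Hypothesis 2b is tested before-after.** It has its own cell-level test at the end of Section 11 (b), using selective inhibitors and supplementation. Those contrasts are not exposed to 20-week drift in the same way.
- **That pERK and calcium shifts would, as written, be credited to the drug.** The before-after wording is attached to the antigen-presenting cells used for Ras/Rho imaging. The stimulated-pERK assay is a feasibility question about an indicator of responsiveness. The calcium analysis is a correlation with treatment response and cytokine profiles. For calcium, the drug-effect goal is stated but no comparison is given for it.
- **That all 50 children would be pooled to claim a lovastatin effect.** No section proposes this.
- **That regression to the mean is a main threat.** No eligibility criterion selects on a signalling marker, so no mean shift is expected from it in the whole sample. Season and infection need not push children in one direction when entry is staggered.
- **That masking is absent.** Section 14 keeps investigators and staff blinded, Section 28 confines unblinding to the pharmacy, and the MMP-9 text has samples coded until results are in.

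It also stands that the drift size is assumed and that Aim 2 is mechanistic work outside the primary and secondary endpoints.

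**Conclusion.** The point holds for the in-vivo drug-effect question: Hypothesis 2a and goals 1 and 2 of the mechanistic studies. No section writes a comparison of these markers by randomised arm, and a shift common to both arms could therefore be read as a lovastatin effect.

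How much this matters depends on drift that the documents do not quantify. At 0.1 SD of change the excess over 5% is small; at 0.2 SD the error rate is about three times nominal. The larger figures need drift of 0.3 SD or more. All of them assume a paired t-test on 25 lovastatin children at two-sided 0.05. They illustrate the mechanism and do not estimate this trial's error rate.

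This is a cheap improvement. It leaves the Aim 1 endpoints untouched, and the samples needed are already scheduled.

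**What to change.** 1. In Section 10, Aim 2, state that the effect of lovastatin on each in-vivo signalling marker at Week 10 and Week 20 will be tested by randomised arm, adjusted for the child's baseline value of that marker.
2. In the mechanistic part of Section 11 (b), replace the parenthesis on baseline and treatment samples with a comparison of change between lovastatin and placebo. Keep the within-child comparison as descriptive.
3. Leave the inhibitor and supplementation experiments as the test of Hypothesis 2b. Keep the responder, ROC, signature and correlation analyses as additional work, since they answer a different question.

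The cost is wording only, with no extra blood or visits. The downside is lower precision than a within-arm change, as shown in the working. Baseline adjustment may recover part of that loss, but the documents give no correlation from which to say how much.
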